#### **14.2.1 Primary safety analysis**

All TEAEs will be summarized descriptively by treatment group, primary system or organ class (SOC), high level term (HLT), and preferred term (PT). This summary will include the exposure adjusted incidence rate (EAIR) with associated 95% confidence interval and the exposure adjusted event rate (EAER).

For EAIR, the numerator will be the total number of subjects experiencing the AE. The denominator will be 100 subject-years; that is, the total summation of individual subject-years at risk up to the first occurrence of the AE for subjects with that AE, and the total subject-years at risk for those subjects not experiencing that AE, divided by 100. Exposure adjusted incidence rates will be presented with a 95% exact confidence interval based upon the Chi-Square distribution (Ulm, 1990).

For EAERs, the numerator will be the number of AEs including repeat occurrences in individual subjects; the denominator will be 100 subject-years. That is, the total summation of individual subject-years at risk divided by 100. No confidence interval will be computed for EAER.

Subject exposure at risk in days will be defined as date of last administration of study medication – date of first administration of study medication +140 days (ie, the duration of the SFU Period). If a subject dies, patient exposure at risk is censored at the date of death. The sum of these exposure days at risk across subjects is converted to years for the EAIR and EAER calculations described above.

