#### 11.1.2 Subject time at risk

The subject time at risk represents the time a subject was at risk for having an AE and will be used to calculate the exposure adjusted incidence rate (EAIR) and exposure adjusted event rate (EAER) as described in [Section 11.2.2](#).

The subject time at risk (days) will be calculated as follows:

$$\text{Time at risk} = (\text{Date of Last PS0018 IMP} - \text{Date of First PS0018 IMP}) + 140 \quad [15]$$

This includes the duration of the SFU Period.

For subjects who switch dose during PS0018, time at risk will be derived in each dose interval and calculated as per equation [13] above, and equation [15] will be applied for the dose in the final dose interval.

In cases where the last clinical contact or last visit occurs prior to completion of the SFU period, the subject time at risk is calculated as follows:

$$\text{Time at Risk} = (\text{Date of Last Contact} - \text{Date of First PS0018 IMP}) + 1 \quad [16]$$

This will apply for the following:

- For subjects that discontinue prematurely (ie, and no SFU data are available), the date of final contact refers to the date of the latest contact with the subject during the study PS0018 after which no further information or data are available. This will be reported on the study termination page of the electronic Case Report Form (eCRF).
- For subjects that have died during the study the date of last contact refers to the date of death

The sum of these exposure days at risk across subjects in the relevant PS0018 dose group is converted to years for the EAIR and EAER calculations described in [Section 11.2.2](#).

Subject-years at risk is defined as the subject time (in days) at risk divided by 365.25. The days at risk and subject years at risk will be listed and summed by PS0018 dose at onset, together with the drug administration information ([Section 11.1.1](#)).

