All summary tables (including those for AESM) will contain the number and percentage of subjects and the number of events where applicable. A subject who has multiple events in the same SOC, HLT and PT will be counted only once in the subject counts but all events will be included. In addition, for all tabulations of AESM, the EAER and EAIR will be reported only for the categories 'Any TEAE'.

The criteria for identifying AESM and additional criteria for reporting AESM are provided in [Section 14.3](#).

Adverse event summaries will be ordered by alphabetical SOC, alphabetical HLT within SOC and decreasing frequency of PT in the 'BKZ 320mg' column for the PS0016 randomized treatment group. In the PS0018 dose at onset tables, the summaries will be presented in a similar manner in decreasing frequency of PT in the 'All BKZ' column.

For tables including only number and percentage of subjects, summaries will be ordered by alphabetical SOC, alphabetical HLT within SOC and decreasing incidence of PT within HLT and SOC in the 'All BKZ' column.

Any adverse events considered ongoing from PS0016 which do not worsen in severity during PS0018 dosing, or starting prior to first PS0018 dose will not be considered treatment emergent in PS0018 and will be tabulated separately.

The AEs will be listed by PS0016 randomized treatment group and include all subjects screened in the ES. The listing will include the onset date/time and outcome date/time of the event (including relative days), the AE duration (derived), dose at onset, days since first dose of study

medication, days since most recent dose of study medication, pattern of event, intensity, relationship, action taken and outcome. In addition the listing will flag AEs that led to discontinuation, TEAEs, AESM, AEs of special interest (as reported on the eCRF) and SAEs.

A glossary of all TEAE terms will be provided including the SOC, HLT, PT and reported term.

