### 14.3 Adverse events of special monitoring

The following AESM are defined for bimekizumab and will be summarized separately as described in [Section 11.2.3](#):

- Major cardiovascular events
- Serious infections, including opportunistic infections and tuberculosis (TB)
- Malignancies including lymphoma
- Cytopenias
- Neuropsychiatric events (in particular, depression and suicide)
- Inflammatory bowel disease
- Anaphylactic reaction (hypersensitivity and anaphylactic reactions)
- Hepatic events and drug-induced liver injury

All AESM tabulations will be presented by Treatment at onset, SOC, HLT and PT, based on the SS, and will include the EAIR and EAER in the 'Any TEAE' categories only.

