#### **14.3.7 Anaphylactic reaction**

Anaphylactic reactions will be summarized together in a stand-alone table with the following incidence rows:

- The first row within the body of the table will be labeled ‘Any hypersensitivity/anaphylactic reaction’ and will represent the overall incidence of subjects who reported at least one hypersensitivity reaction or at least one anaphylactic reaction.
- The second row within the body of the table will be labeled ‘Any hypersensitivity reaction’ and will represent the overall incidence of subjects who reported at least one hypersensitivity reaction.
- The third row within the body of the table will be labeled ‘Any anaphylactic reaction’ and will represent the overall incidence of subjects who reported at least one anaphylactic reaction.

Following these three overall incidence rows, all TEAEs that have been identified as either a hypersensitivity reaction or an anaphylactic reaction will be summarized by SOC, HLT and PT (these will not be presented by subcategory).

Hypersensitivity reactions and anaphylactic reactions will be identified as follows:

- **Hypersensitivity reactions:** all TEAEs with onset (start date/time) within 24 hours after any administration of study medication, which code to a PT which contains the term 'hypersensitivity' will be considered to be a hypersensitivity reaction and included in the summary table
- **Anaphylactic reactions:** An algorithmic approach will be used to identify TEAEs that are considered to be anaphylactic reactions. Preferred terms are separated into 4 distinct categories (A, B, C, D) prior to the algorithmic approach being applied.

All TEAEs with onset (start date/time) within 24 hours after any administration of study medication, and which fulfill any of the 3 criteria described in [Section 14.3.7.1](#) will be included in the summary table.

Any TEAEs with missing start time will be assumed to have occurred at the time of or after dosing for this purpose, if the event date is on the same day as a dosing date.

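### Hypersensitivity and anaphylaxis rates count events only within 24 hours of a dose but divide by time at risk that includes a 140-day tail, so the 160mg and 320mg columns can differ at equal per-dose risk

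*SAP*

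**What the plan says.** SAP 14.3.7 applies the same window to both reaction types. Hypersensitivity reactions are "all TEAEs with onset (start date/time) within 24 hours after any administration of study medication, which code to a PT which contains the term" hypersensitivity. Anaphylactic reactions are "All TEAEs with onset (start date/time) within 24 hours after any administration of study medication, and which fulfill any of the 3 criteria" of the algorithm in 14.3.7.1.

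SAP 14.3 states "All AESM tabulations will be presented by Treatment at onset, SOC, HLT and PT, based on the SS, and will include the EAIR and EAER", restricted to the overall (Any TEAE) rows. SAP 11.2.3 repeats the rule: "for all tabulations of AESM, the EAER and EAIR will be reported only for the categories" of that kind. Neither section exempts the hypersensitivity/anaphylaxis table.

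The denominator comes from SAP 11.1.2. Equation [15] is last dose minus first dose plus 140 days, and the SAP adds "This includes the duration of the SFU Period". Time is cut at last contact or death when that comes earlier (equation [16]). For subjects who change dose, "time at risk will be derived in each dose interval and calculated as per equation [13] above, and equation [15] will be applied" only to the final interval; the earlier intervals get last minus first dose plus 1 day.

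Under SAP 11.2.2, EAER divides by all of this time. EAIR does so for subjects without the event, and stops at first onset for subjects with it. Columns are 160mg Q4W, 320mg Q4W and All BKZ, by dose at onset. SAP 11.2.3 also plans the number and percentage of subjects and the number of events.

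**The concern.** A rate per subject-year is easiest to interpret when an event could be counted at any moment of the time in the denominator. Here the case definition allows an event only in the day after each dose. The days between doses, and nearly all of the 140-day tail, add to the denominator but can never add to the numerator.

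The SAP otherwise treats these events as triggered by the dose. Section 11.2.1 assigns an anaphylactic reaction of uncertain timing on a dose-change day to the dose given that day, and 14.3.7 assumes that an untimed reaction on a dosing day occurred at or after dosing. Only the denominator departs from this logic.

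At stake is the comparison of the dose columns for a reaction tied to dosing, in a study with a secondary objective on the safety of increasing the dose. A reader could take a difference between columns as a dose effect when it reflects which column received the follow-up tail.

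**Working it through.** **Inputs.**
- Dosing visits for a completer: 12, at Weeks 0 to 44 every 4 weeks (SAP Section 7; protocol Table 5–1). The visit list in SAP 11.1.1 omits Week 36, and these passages must be reconciled; 12 is used here.
- Time at risk: equations [15] and [13] of the SAP, with [13] read as first to last dose within the interval.
- Planned enrolment: up to 45 (SAP 2.4).
- Assumptions not in the documents: 10 of 45 subjects adjust dose, everyone completes treatment and follow-up, and the reaction risk p per dosing visit is the same at both doses.

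**Step 1, the plan's own figure.** 44 × 7 + 140 = 448 days = 64 weeks, which matches the maximum study duration in SAP 3.2.1.2. The countable share for a nonadjusting completer is 12/448 = 2.7%.

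**Step 2, what the rate measures.** Expected EAER = 100 × p × doses ÷ (days/365.25). A nonadjusting completer has 12 ÷ (448/365.25) = 9.8 doses per subject-year. At an assumed p of 0.2%, 0.5% and 1%, the EAER is 1.96, 4.89 and 9.78. So at fixed dosing the rate is proportional to p. The expected EAIR at p = 0.5% is 4.95 against an EAER of 4.89, so stopping at first onset changes little.

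**Step 3, dose intervals of a Week 12 switcher.**
- No return: 160mg has 3 doses in 2 × 28 + 1 = 57 days; 320mg has 9 doses in 8 × 28 + 140 = 364 days.
- Return at Week 24: 320mg has 3 doses in 57 days; 160mg has 3 + 6 = 9 doses in 57 + (5 × 28 + 140) = 337 days.

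**Step 4, the columns.** The 35 nonadjusters give 35 × 12 = 420 doses in 35 × 448 = 15,680 days on 160mg. With r of the 10 switchers returning:
- 320mg: 9(10 − r) + 3r doses in 364(10 − r) + 57r days
- 160mg: 420 + 3(10 − r) + 9r doses in 15,680 + 57(10 − r) + 337r days

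With equal p, the rate ratio is the ratio of doses per day.

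| r | 320mg doses/days | 160mg doses/days | 320/160 ratio |
|---|---|---|---|
| 0 | 90/3,640 | 450/16,250 | 0.89 |
| 4 | 66/2,412 | 474/17,370 | 1.00 |
| 6 | 54/1,798 | 486/17,930 | 1.11 |
| 10 | 30/570 | 510/19,050 | 1.97 |

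**Step 5, later switching without return.**
- All 10 at Week 24: (60/2,800) ÷ (480/17,090) = 0.76.
- All 10 at Week 40: (20/1,680) ÷ (520/18,210) = 0.42.

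**Step 6, reading of equation [13].** If a non-final interval ran to the day of the dose change (84 days instead of 57):
- r = 0: (90/3,640) ÷ (450/16,520) = 0.91.
- r = 10: (30/840) ÷ (510/19,320) = 1.35.

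The size changes, but the two paths still point in opposite directions.

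**Step 7, the alternative denominator.** Per 100 administrations, equal p gives the same expected figure in both columns: 0.5 at p = 0.5%. The SAP rates with r = 0 would be 100 × 0.005 × 450 ÷ (16,250/365.25) = 5.06 for 160mg and 100 × 0.005 × 90 ÷ (3,640/365.25) = 4.52 for 320mg. The expected numbers of events behind them are 450 × 0.005 = 2.25 and 90 × 0.005 = 0.45.

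**The case against.** The best defence is that reactions meeting a 24-hour case definition, per 100 subject-years of follow-up, are a valid descriptive quantity. It uses the protocol's own definition of time at risk (14.2.1) and the scale of the other AESM tables. Both doses are given every 4 weeks, so on-treatment dosing frequency does not differ. Subject counts, percentages and event counts are already planned. Every administration is listed (SAP 11.1.1), and the AE listing shows dose at onset and days since the most recent dose, so a per-dose reading can be recovered by hand. Dose adjustment is examined mainly through the TEAE and serious TEAE summaries by adjustment group. Nothing is tested.

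Much of this stands. It is a good reason to keep EAIR and EAER, and it limits the damage to the secondary objective. It does not rescue the comparison between columns, because the tail and the interval rule still load the two doses unequally. The planned percentages do not fill the gap either, since they also depend on doses received. At p = 0.5%, 1 − 0.995^k gives 5.8% after 12 doses, 4.4% after 9 and 1.0% after 2.

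A reader might go further and infer that these rates reflect dosing density rather than risk, or that 320mg will always look safer. The documents support neither. The rate is proportional to per-dose risk at fixed dosing. The second inference requires adjusters to finish on 320mg, whereas protocol 5.1 allows return to 160mg and both documents define multiple adjusters.

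**Conclusion.** The mismatch between numerator and denominator is in the text, and no section exempts this table. The rates mix per-dose risk with doses per subject-year, and the dose columns are not cleanly comparable. For switching at Week 12, the time point named in the secondary objective, the 320/160 ratio at equal risk runs from 0.89 to 1.97 as the number returning at Week 24 goes from none to all 10. Neither direction can be presumed. The more extreme low value of 0.42 needs all 10 to switch at Week 40, never return and complete.

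These ratios rest on the assumed 35/10 split, full completion, a common switch week and the within-interval reading of equation [13]; the documents give no expected switching pattern. The priority is low because the table is descriptive, few events are expected in up to 45 subjects, and the subject and event counts will be shown regardless.

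**What to change.** In the SAP 14.3.7 table, add reactions per 100 administrations, by the dose given at the triggering visit. Define one administration as one dosing visit, whether it takes 1 or 2 injections. Add an exact 95% CI for the proportion of subjects with a reaction. Using the triggering visit also settles untimed hypersensitivity events on a dose-change day, which the 11.2.1 exception does not clearly cover.

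In 14.3 and 11.2.3, state that for this table the per-administration rate, and not EAIR or EAER, is the basis for comparing dose columns. EAIR and EAER may stay for consistency with the other AESM tables.

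The cost is a few lines of SAP text and one table shell. The number of administrations is already in the drug administration data. The downside is one extra row on a different scale from the rest of the AESM output.

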#### 14.3.7.1 Anaphylactic reaction algorithm

The SMQ = 'anaphylactic reaction' consists of 3 parts:

A **narrow search** containing PTs that represent core anaphylactic reaction terms. If a subject reports any TEAE which codes to a PT included in Category A, then the event will be flagged as an anaphylactic reaction and summarized as such in the table.

– Category A

5. Anaphylactic reaction
6. Anaphylactic shock
7. Anaphylactic transfusion reaction
8. Anaphylactoid reaction
9. Anaphylactoid shock
10. Circulatory collapse
11. Dialysis membrane reaction
12. Kounis syndrome
13. Shock
14. Shock symptom
15. Type I hypersensitivity

- A **broad search:** If a subject reports any TEAE which codes to a PT included in Category B **AND** reports any TEAE which codes to a PT included in Category C, **and both TEAEs have the same start date**, then both events will be flagged as anaphylactic reactions and summarized as such in the table.

– **Category B**

1. Acute respiratory failure
2. Asthma
3. Bronchial oedema
4. Bronchospasm
5. Cardio-respiratory distress
6. Chest discomfort
7. Choking
8. Choking sensation
9. Circumoral oedema
10. Cough
11. Cyanosis
12. Dyspnoea
13. Hyperventilation
14. Irregular breathing
15. Laryngeal dyspnoea
16. Laryngeal oedema
17. Laryngospasm
18. Laryngotracheal oedema
19. Mouth swelling
20. Nasal obstruction
21. Oedema mouth
22. Oropharyngeal spasm
23. Oropharyngeal swelling
24. Respiratory arrest
25. Respiratory distress
26. Respiratory dyskinesia
27. Respiratory failure
28. Reversible airways obstruction
29. Sensation of foreign body
30. Sneezing
31. Stridor

- 32. Swollen tongue
- 33. Tachypnoea
- 34. Throat tightness
- 35. Tongue oedema
- 36. Tracheal obstruction
- 37. Tracheal oedema
- 38. Upper airway obstruction
- 39. Wheezing

– **Category C**

- 1. Allergic oedema
- 2. Angioedema
- 3. Erythema
- 4. Eye oedema
- 5. Eye pruritis
- 6. Eye swelling
- 7. Eyelid oedema
- 8. Face oedema
- 9. Flushing
- 10. Generalised erythema
- 11. Injection site urticaria
- 12. Lip oedema
- 13. Lip swelling
- 14. Nodular rash
- 15. Ocular hyperaemia
- 16. Oedema
- 17. Periorbital oedema
- 18. Pruritis
- 19. Pruritis allergic
- 20. Pruritis generalised
- 21. Rash
- 22. Rash erythematous
- 23. Rash generalized

24. Rash pruritic
25. Skin swelling
26. Swelling
27. Swelling face
28. Urticaria
29. Urticaria papular

– **Category D**

1. Blood pressure decreased
2. Blood pressure diastolic decreased
3. Blood pressure systolic decreased
4. Cardiac arrest
5. Cardio-respiratory arrest
6. Cardiovascular insufficiency
7. Diastolic hypertension
8. Hypotension

An **algorithmic approach**: If a subject reports any TEAE which codes to a PT included in Category D **AND** reports (either a TEAE which codes to a PT included in Category B **OR** a TEAE which codes to a PT included in Category C), **and both TEAEs have the same start date**, then both events will be flagged as anaphylactic reactions and summarized as such in the table.

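### Category D of the SAP's anaphylaxis algorithm holds one raised-pressure term among seven low-pressure or circulatory-failure terms, so raised diastolic pressure can help trigger an anaphylaxis flag

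*SAP*

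**What the plan says.** SAP Section 14.3.7 limits the anaphylaxis search to TEAEs that start within 24 hours after any dose. A TEAE with no start time on a dosing day is taken to have begun at or after dosing.

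Section 14.3.7.1 then gives three routes to a flag, which it attributes to the MedDRA query for anaphylactic reaction:

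- any Category A term;
- a Category B term and a Category C term with the same start date;
- a subject who "reports any TEAE which codes to a PT included in Category D" and also has a Category B or Category C event with the same start date. Both events are then flagged.

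Category D has eight terms. Among them are "Blood pressure decreased", "Blood pressure diastolic decreased", "Blood pressure systolic decreased", "Cardiac arrest" and "Cardio-respiratory arrest". Item 7 is "Diastolic hypertension".

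Sections 11.2.3 and 14.3 place flagged events in a table by dose at onset, with exposure-adjusted rates (EAIR and EAER) for the any-TEAE rows. SAP Amendment 1 (Section 15.1) leaves the list unchanged.

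**The concern.** Category D supplies the cardiovascular part of the definition, and seven of its eight terms concern a fall in pressure or loss of circulation. A raised-pressure term does not fit that role, and it is operative: the rule treats it exactly as it treats hypotension. Several of the terms it can pair with are common and non-specific, such as cough, sneezing, erythema and rash.

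No review step is described that would catch a false match. The SAP describes external adjudication for major cardiovascular events and for suicidal ideation and behavior, physician and committee review for case-by-case opportunistic infections, and adjudication for potential drug-induced liver injury. For anaphylaxis the term lists decide alone. At stake are the count of a rare and closely watched event and, in one narrow situation, the dose to which the events are attributed.

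**Working it through.** The plan states no figure to reproduce. The check is a reading of the list, a trace of the rule, and arithmetic for what one false case would look like.

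**1. Direction of each Category D term**

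| Item | Term | Direction |
|---|---|---|
| 1 | "Blood pressure decreased" | low pressure |
| 2 | "Blood pressure diastolic decreased" | low pressure |
| 3 | "Blood pressure systolic decreased" | low pressure |
| 4 | "Cardiac arrest" | circulatory failure |
| 5 | "Cardio-respiratory arrest" | circulatory failure |
| 6 | cardiovascular insufficiency | circulatory failure |
| 7 | "Diastolic hypertension" | **raised pressure** |
| 8 | hypotension | low pressure |

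One of the eight is out of pattern.

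**2. What item 7 can pair with.** Category B lists 39 terms and Category C lists 29, so item 7 has 39 + 29 = 68 possible partners. Across Category D there are 8 × 68 = 544 pairs, of which item 7 supplies 68. This counts combinations. It says nothing about how often they occur.

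**3. When item 7 creates a new case.** It adds a subject only if that subject is not already flagged by a Category A term, by a same-date B and C pair, or by another Category D term. The simplest example is a TEAE of raised diastolic pressure and a TEAE of cough, with the same start date, within 24 hours of an injection.

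**4. The timing condition.** Blood pressure is measured at every visit before dosing (Protocol Section 9.8.3; SAP Section 11.4.1). If a raised pre-dose reading is reported as an AE without a start time, SAP Section 14.3.7 treats it as starting at or after that day's dose, and it meets the 24-hour condition.

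**5. Size of one false case, both doses combined.** Inputs: up to 45 subjects (Protocol Section 14.7); doses from Week 0 to Week 44 (SAP Section 7); time at risk equal to last dose minus first dose plus 140 days (SAP equation 15). Assume that all 45 enrol, complete dosing and stay on one dose.

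- Incidence: 1/45 = 2.2%, against 0.
- Time at risk per subject: 44 × 7 + 140 = 448 days. Total: 45 × 448 / 365.25 = 55.2 subject-years.
- EAIR: the affected subject contributes time only up to onset, between about 0 and 308 days. The denominator is therefore 44 × 448 = 19,712 days plus 0 to 308 days, which is 54.0 to 54.8 subject-years. The rate is 100/54.8 to 100/54.0, or 1.8 to 1.9 per 100 subject-years.
- EAER: both events of the pair are flagged, so 100 × 2/55.2 = 3.6 per 100 subject-years.

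With fewer subjects, or within a single dose column, the same case would give larger figures.

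**6. Effect on dose at onset.** SAP Section 11.2.1 assigns a TEAE of unclear timing on a dose-change day to the dose just completed. Injection-site reactions and anaphylactic reactions as defined in Section 14.3.7.1 are exceptions and go to the dose given that day. A false flag therefore moves the flagged events of unclear timing (up to two per pair) between the 160mg and 320mg columns. A missing start time can satisfy the 24-hour condition and also make the timing unclear. The combined column is unaffected.

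**The case against.** The strongest reply is that this is a probable text slip in an appendix with a remote effect. Much of that stands.

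- **The intended term is unknown.** The MedDRA 19.0 query is not reproduced, so the documents show only that item 7 is inconsistent with its neighbours. They do not establish what the entry should be.
- **The event is rare.** A false case needs an AE coded to this exact term, a same-date partner, and onset within 24 hours of a dose. Nothing in the documents gives a frequency, so 2.2% is the size of one case and not an expected value.
- **A false case would be visible.** Flagged TEAEs are tabulated by preferred term, so the raised-pressure term would appear by name in the anaphylaxis table. A reader could see the cause, although the summary rows would still count the case.

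Two stronger readings are tempting, and the documents do not support them.

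- **That true cases of low diastolic pressure would be missed.** Items 1, 2 and 8 already cover low pressure in general and low diastolic pressure by name. Whether some further term is absent depends on dictionary content that is not shown.
- **That the irregular spellings in Category C, such as "Pruritis generalised", would cause cases to be dropped.** That assumes a program that matches typed strings exactly. The SAP speaks of events coding to preferred terms, fixes MedDRA 19.0 and names the query, and it describes no such matching. The spellings are an editorial matter.

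What the reply does not remove is that the list is an operative instruction and, followed as written, can classify raised diastolic pressure as part of an anaphylactic reaction.

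**Conclusion.** The point holds: the list is wrong as written, at low severity. Item 7 contradicts the rest of Category D, and no other text explains it, corrects it or provides a review that would catch a false match. A false case would inflate the anaphylaxis summary: one in up to 45 subjects is 2.2%, or 1.8 to 1.9 per 100 subject-years for EAIR under full enrolment and completion. On a dose-change day with unclear timing, it could also shift the events between dose columns, which touches the comparison behind the dose-increase objective.

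A reader might infer that the study's safety conclusion is at risk. The documents do not support that. The primary safety variable is exposure-adjusted TEAE incidence, and these events are counted there whether or not they carry the anaphylaxis flag. The direct effect is confined to one special-monitoring table, its rates, the listing flag and the narrow dose-at-onset case.

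The conclusion rests on reading the Category D rule literally. If the program takes its terms from the dictionary and the dictionary differs from the typed list, the output might be right while the SAP text remains wrong.

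**What to change.** Before database lock, check Category D item 7 against the MedDRA 19.0 anaphylactic reaction query that the SAP names. Correct or remove the term so that no raised-pressure event can trigger the flag, record the outcome in a SAP amendment, and confirm that the program uses the corrected list. Tidy the Category C spellings in the same pass.

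The cost is one dictionary lookup and a short text correction. No data collection, sample size or other analysis changes.
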